4 STUDY ENDPOINTS

4.1 Safety Endpoints

- Frequency and severity of treatment-emergent AEs/SAEs.
- Relationship of AEs to study drug (eg, either acalabrutinib, pembrolizumab, or both).
- Change of laboratory parameters from baseline over time.
- Vital sign assessments, ECGs, and physical examinations

4.2 Efficacy Endpoints

- Response rate
- Duration of response
- Progression-free survival
- Time-to-next treatment
- Overall survival

4.3 PD or Biomarker Analysis

Additional PD and biomarker analyses may be performed, as deemed appropriate.

5 HYPOTHESES AND MULTIPLICITY

No formal statistical hypothesis will be tested. The clinical hypothesis is that acalabrutinib and pembrolizumab is safe and effective in subjects with hematologic malignancies.

6 ANALYSIS SUBSETS

6.1 All Treated Population

The safety analyses and primary efficacy analyses will be performed on the All-treated population, defined as all enrolled subjects who receive ≥ 1 dose of any study drug (either acalabrutinib or pembrolizumab).

6.2 Efficacy-evaluable Population

All subjects in the All-treated population who have ≥ 1 evaluable response assessment after the first dose of study drug (either acalabrutinib or pembrolizumab). Sensitivity analyses for efficacy will be carried out on the Efficacy-evaluable population.

7 INTERIM ANALYSIS

No formal interim analysis was planned.

8 MISSING VALUES

No imputation of values for missing data will be performed except that missing or partial start and end dates for AEs and concomitant medication will be imputed according to prespecified, conservative imputation rules. Subjects lost to follow-up (or drop out) will be included in statistical analyses to the point of their last evaluation.

Imputation of partial dates will be made for AE onset and stop dates, start and end dates of concomitant medication, start date of subsequent anticancer therapy, date of initial diagnosis and death date. If dates are completely missing, no imputation will be made. For any partial date with missing year, no imputation will be made.

The general rule for imputation is:

- If only day is missing, then the 15th of the month will be used.
- If only year is present, then June 30th will be used.

If such imputation date for initial diagnosis is on or after date of first dose, the date of first dose – 1 will be used. If such imputed date for subsequent anticancer therapies is before date of last dose, the date of last dose + 1 will be used.

If the imputed date is for an AE start date and is in the same year and month as the first dose date but before the first dose date, then the first dose date will be used, or if the imputed AE start date is after the AE end date, then the AE end date will be used. If the imputed date is for an AE start date and is in the same year and month as but after the last dose date + 30 days, then the last dose date + 30 days will be used.

If the imputed date is for an AE end date and is after the death date, the date of death will be used, or if the imputed AE end date is before the AE start date, the AE start date will be used.

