# 5.4 MISSING DATA HANDLING

No imputation of values for missing data will be performed except that missing or partial start and end dates for AEs and concomitant medication will be imputed according to prespecified, conservative imputation rules. Subjects lost to follow-up (or drop out) will be included in statistical analyses to the point of their last evaluation.

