9.5.2 Prior and Concomitant Medications Received for Indications Other than Target Disease

Data reported on concomitant CRF page will be used. Medications started or ended prior to first dose will be considered as prior treatment. Concomitant therapy is defined as all medications used on or after the first dose, through the treatment phase, and for 30 days following the last dose of study drug. Using this definition, a medication can be classified as both prior and concomitant. Start date and end date will be imputed based on the rules provided in Section **12.1.** of the SAP. Medications with completely missing start and stop dates will be considered as concomitant medications.

Prior and concomitant medications other than antineoplastic agents or other systemic therapies after enrollment will be summarized by the World Health Organization (WHO) Drug Dictionary therapeutic class, pharmacological class, and preferred term by each disease area.

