9.7.1 Adverse Events

The Medical Dictionary for Regulatory Activities (MedDRA) will be used to code all AEs to a system organ class and a preferred term. The severity of the AE will be assessed by National Cancer Institute (NCI) Common Terminology Criteria for Adverse Events (CTCAE) Version 4.03 or higher. Drug-related AEs are those assessed by investigator as related.

Treatment-emergent AEs are defined as those events that occur (actual or imputed start date) on or after the first dose of study drug, through the treatment phase, and within 30 days following the last dose of study drug.

Treatment-emergent AEs will be summarized by system organ class and preferred terms in descending order of frequency, by NCI toxicity grade and by relationship to study drug. The same summary will be provided for serious treatment-emergent AEs and drug-related serious treatment-emergent AEs, treatment-emergent AEs leading to treatment discontinuation, dose reductions and dose withheld.

Death information is reported in the study exit CRF for all deaths. Incidences of deaths are to be reported, along with the primary cause of death.

AE by subject listing and death listing will be provided.

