12 APPENDICES

12.1 Study day

The study day will be calculated in reference to the date of first dose date. Study Day 1 is defined as the date of first dose of any study drug. For assessments that occur on or after first dose date, study day is defined as (date of assessment – date of first dose + 1). For assessments that occur prior to first dose date, study day is defined as (date of assessment – date of first dose). There is no Study Day 0.

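### SAP Section 8 dates a year-only adverse event onset to 30 June, and its first-dose guard can never correct that date, so some on-treatment events drop out of the treatment-emergent tables; imputed death dates have no lower bound

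*SAP*

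**What the plan says.** SAP Section 8 imputes a date with only the day missing to the 15th of the month. For a date with month and day missing, "If only year is present, then June 30th will be used". The list of imputed dates includes AE onset and stop dates and the death date.

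Three guards then apply to an imputed AE onset:

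- It becomes the first dose date if it "is in the same year and month as the first dose date but before the first dose date".
- It becomes the AE end date if it is later than the AE end date.
- It becomes last dose + 30 days if it "is in the same year and month as but after the last dose date + 30 days".

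For AE end dates, "if the imputed AE end date is before the AE start date, the AE start date will be used". Initial diagnosis and subsequent therapy also have bounds. The death date has none, in Section 8, in 9.6.5 or in 12.4.

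SAP 9.7.1 classes an AE as treatment-emergent by its start ("actual or imputed start date) on or after the first dose of study drug") and up to 30 days after last dose. The AE summary tables are built on that class.

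Protocol 5.4 and SAP Section 8 both describe the AE and medication dates as "imputed according to prespecified, conservative imputation rules".

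SAP 9.5.2 sends the reader elsewhere for date rules ("Start date and end date will be imputed based on the rules provided in Section" 12.1). Section 12.1 only defines study day: "Study Day 1 is defined as the date of first dose of any study drug".

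**The concern.** Safety is the primary objective. When an AE's timing is uncertain, a conservative rule counts it as treatment-emergent. SAP Section 8 evidently intends this, since it has a floor at first dose and a ceiling at last dose + 30 days. But both guards test year and month, and a year-only date has no month of its own. It is given June by convention and the guards then treat that June as information.

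The result is that an on-treatment AE can be removed from the treatment-emergent tables by system organ class, grade, relationship, seriousness and action taken. This also sits badly with data collection. Before first dose, Protocol 6.2.1 asks for serious AEs and Protocol 6.2.6 for certain events of clinical interest, but neither asks for non-serious AEs in general. An ordinary non-serious AE on the form should therefore be post-dose, yet the rule can date it before dosing.

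The missing floor for deaths affects secondary endpoints. It does not favour the drug, but it can produce impossible survival times.

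**Working it through.** The plan gives no figure on this point to reproduce, so the check applies the rules literally.

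**1. First-dose guard, no assumptions needed.** For a year-only onset the guard needs a first dose in June that is later than 30 June, and no such date exists. Over every possible first-dose date in 2015, 2016 and 2017, with onset year equal to first-dose year, the guard acted 0 times. The onset fell before first dose for all 184 dates from 1 July to 31 December and for none from 1 January to 30 June. Example: first dose 1 September 2016, onset recorded as 2016, imputed 30 June 2016, 31 + 31 + 1 = 63 days before first dose. The other two guards only move the date earlier, so neither can rescue it.

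**2. Day-missing onsets, for comparison.** With onset in the first-dose month, the guard acts on 185 first-dose dates (186 in a leap year) and 0 events are lost.

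**3. Last-dose guard.** If last dose + 30 days falls in January to May of the onset year, 30 June is after the window but in a different month, so the guard does not act. Example: last dose 10 February 2017, window closes 12 March 2017, onset 2017 becomes 30 June 2017, 110 days too late. A complete AE end date usually pulls it back; a missing or year-only end date does not.

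**4. Illustrative size.** Inputs: longest exposure 30.2 months and median 3.4 months at 3 September 2017 (Protocol 1.4.2.1); enrolment closed May 2017 (Protocol 5.1). 30.2 months before 3 September 2017 is 27 February 2015. Assumptions, none stated in the documents: first doses evenly spread over 27 February 2015 to 31 May 2017 (825 days, 368 of them in July to December), onsets uniform over first dose to last dose + 30 days, and one common exposure. Pairs enumerated: 825 × (103 + 30) = 109,725 and 825 × (365 + 30) = 325,875.

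| Year-only onset truly inside the window | 103 days' exposure | 365 days' exposure |
|---|---|---|
| Dated before first dose | 28.6% | 10.4% |
| Dated after window, end date missing or year-only | 20.7% | 9.5% |
| Dated after window, complete end date 7 / 14 / 30 days after onset | 0.3 / 1.0 / 4.2% | 0.1 / 0.4 / 1.8% |
| Either, under the rule proposed below | 0% | 0% |

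The figures depend on the assumptions: if onsets are confined to the first 28 days, 41% are dated before first dose at either exposure.

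**5. Deaths.** First dose 1 August 2016, last known alive 20 November 2016. Death recorded as 2016 becomes 30 June 2016: 32 days before first dose, 143 days before last known alive, so overall survival is negative. Death recorded as November 2016 becomes 15 November, 5 days before last known alive. For day-missing deaths, assume a uniform day of death and a uniform gap of 0 to 21 days since last contact. In a 31-day month the share dated too early is (1 + … + 16)/(22 × 31) = 136/682 = 19.9%. In a 30-day month it is 120/660 = 18.2%. Over a calendar year it is 19.0%, and for gaps of 0 to 30 and 0 to 84 days 13.5% and 4.9%.

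**The case against.** **Few dates will be affected.** AEs are assessed weekly for 8 weeks and then every 3 weeks while on combination treatment, and each is recorded with start and end dates (Protocol 3.0 and 6.2.2). The commoner case, a missing day, is handled correctly. The analyses are descriptive, with no formal test (SAP Section 5). This stands, and it limits the size of the point.

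**A reader might infer that lost events vanish from every summary and survive only in the listing.** The documents do not support that. Laboratory abnormalities still reach the shift tables in SAP 9.7.2, which use laboratory data and not AE onset. Dose reductions and interruptions are summarised under 9.5.3, discontinuation reasons under 9.2, and deaths separately under 9.7.1. The listing is the only remaining place for other, mainly non-laboratory, events without such consequences.

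**A reader might infer that the rule contradicts Protocol 6.2.1.** It does not. That section governs collection, not analysis dates, and Protocol 6.2.6 also takes some non-serious events of clinical interest before dosing. The two fit poorly together, and no more can be said.

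**The death problem is mostly theoretical.** Deaths from causes other than progression are serious AEs reportable within 24 hours (Protocol 6.2.5), all deaths go on the study exit form (SAP 9.7.1), and survival contact is about every 12 weeks (Protocol 4.4). A negative survival time would be noticed. This also stands, but noticing it after database lock still leaves the correction unspecified.

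**Conclusion.** The point holds on the text of SAP Section 8, and no other section repairs it. What is firm is the all-or-nothing statement: for a year-only onset in the first-dose year, 100% are dated before first dose if first dose is 1 July or later, and 0% if it is by 30 June. That is the reverse of a conservative rule, on the primary objective.

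The 29% and 10% figures are illustrations per affected event, under even accrual, uniform onsets and one common exposure. They should not be read as the share of this trial's AEs that would be lost. The number of year-only onsets is not given and is probably small.

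For deaths, a year-only date in the first-dose year with first dose on or after 1 July gives negative overall survival. It gives negative progression-free survival only where death is the event under SAP 12.3, that is, without documented progression and before new therapy. A day-missing death can precede the last date known alive. These cases should be rare.

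The correction is small, but the SAP should carry it.

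**What to change.** In SAP Section 8:

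1. **Year-only AE onsets: apply both guards on the year alone, in this order.** Take 30 June. If last dose + 30 days falls in the onset year and is earlier, use that. Cap at the AE end date, ignoring an end date that is itself year-only. Then, if the onset year is the first-dose year and the date is before first dose, raise it to first dose, unless the known parts of the end date show that the AE ended before first dose. A year-only end date must be ignored because it also becomes 30 June and would pull the onset back before first dose; the existing end-date guard then raises that end date to the onset. Keep the current rule for day-missing onsets.
2. **Deaths: use the later of the imputed date and the last date known alive.** This stays within the known month or year and cannot precede first dose.
3. **Correct the cross-reference in SAP 9.5.2** from 12.1 to Section 8.

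The cost is a few lines of text and programming, plus some over-counting in the conservative direction. Under the assumptions above and with no end date, year-only serious AEs that truly began in the 28 days before first dose would be classed treatment-emergent in about 96% of cases, against about 50% now. With a complete end date 7 or 14 days after onset, the change is from 14% to 25% or from 27% to 49%. Year-only serious AEs that truly began 31 to 90 days after last dose, which Protocol 6.2.1 collects for pembrolizumab, would go from about 50% to 93%. Both groups should be few.

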9.6.3 Progression-free Survival

Progression-free survival (PFS) is defined as the interval from the first dose date of acalabrutinib or pembrolizumab to the earlier of the first documentation of objective disease progression or death from any cause. Subjects who had the event after the start of subsequent therapy, or who are progression-free and alive at the time of data cutoff, or have unknown status will be censored at the time of their last disease assessment on or before the start of subsequent therapy and data cut-off. Subjects with no post baseline disease assessment will be censored on Day 1. The censoring rules for primary and sensitivity analyses of PFS are summarized [Appendix 14.4](#).

The summary of PFS including the mean, minimum, maximum, median, Q1 and Q3 are provided for all the responders for each disease group.

Summary of K-M estimates of PFS and 95% CIs as proper for each disease group

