12.2 Censoring Rules for Duration of Response

Situation	Outcome	Date	Event Description/ Censoring Reason
Progression documented between scheduled visits on or before receiving subsequent anticancer therapy or data cutoff, whichever occurred first	Event	Earliest date of disease assessment documenting progression	PD
Death without documented PD on or before receiving subsequent anti-cancer therapy or data cutoff, whichever occurred first	Event	Date of Death	Death
New anti-cancer treatment Started before PD or death for subjects with or without documented PD or death and before data cutoff	Censored	Date of last adequate disease assessment prior to subsequent anti-cancer treatment	New anti-cancer therapy
No documented PD or death at the time of data cutoff and subject not received subsequent anti-cancer therapy or subsequent anti-cancer therapy start date after the data cutoff	Censored	Date of last adequate disease assessment on or before data cutoff	Data cutoff
Withdrew consent before documented PD or death	Censored	Date of last adequate disease assessment	Withdrew consent
Lost to follow-up before documented PD or death	Censored	Date of last adequate disease assessment	Lost to follow-up

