12.3 Censoring Rules for Progression-free Survival

Situation	Outcome	Date	Event Description/ Censoring Reason
Progression documented between scheduled visits on or before receiving subsequent anticancer therapy or data cutoff, whichever occurred first	Event	Earliest date of disease assessment documenting progression	PD
Death without documented PD on or before receiving subsequent anti-cancer therapy or data cutoff, whichever occurred first	Event	Date of Death	Death
death before first adequate disease assessment	Event	Date of Death	Death
New anti-cancer treatment Started before PD or death for subjects with or without documented PD or death and before data cutoff	Censored	Date of last adequate disease assessment prior to subsequent anti-cancer treatment	New anti-cancer Therapy
No documented PD or death at the time of data cutoff and subject not received subsequent anti-cancer therapy or subsequent anti-cancer therapy start date after the data cutoff	Censored	Date of last adequate disease assessment on or before data cutoff	Data cutoff
Withdrew consent before documented PD or death	Censored	Date of last adequate disease assessment	Withdrew consent
Lost to follow-up before documented PD or death	Censored	Date of last adequate disease assessment	Lost to follow-up
No post-baseline adequate disease assessments	Censored	Date of first dose	No post-baseline adequate disease assessments
No baseline disease assessments	Censored	Date of first dose	No baseline disease assessment

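### A partial start date for new anticancer therapy can be imputed to before a documented progression, turning a PFS or DOR event into censoring; overall size and net direction are unknown

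*SAP*

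**What the plan says.** SAP section 8 lists the dates that are imputed when partial, including "start date of subsequent anticancer therapy, date of initial diagnosis and death date". When the month is known the rule is "If only day is missing, then the 15th of the month will be used"; otherwise it is "If only year is present, then June 30th will be used". One check applies to the new-therapy date: "If such imputed date for subsequent anticancer therapies is before date of last dose, the date of last dose + 1 will be used". Nothing compares that date with documented progression or with death. The same section does cross-check AE dates: an imputed AE start is compared with AE end, and an imputed AE end with death and AE start.

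The therapy date then decides between event and censoring. In SAP 12.3 the condition for a PFS event is "Progression documented between scheduled visits on or before receiving subsequent anticancer therapy or data cutoff, whichever occurred first". The competing row, which leads to censoring, is "New anti-cancer treatment Started before PD or death for subjects with or without documented PD or death and before data cutoff". SAP 12.2 has the same two rows for DOR and dates the censoring at "Date of last adequate disease assessment prior to subsequent anti-cancer treatment". The text of SAP 9.6.2 and 9.6.3 agrees, censoring "Subjects who had the event after the start of subsequent therapy".

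**The concern.** A fixed mid-period date says nothing about whether therapy came before or after progression, yet the censoring tables treat it as if it did. A subject who progressed off drug and then started new therapy later in the same month can be recorded as having started first. The progression is then disregarded and follow-up ends at the scan before. Appendix 5 of the protocol places scans at Week 8, Week 19 and then every 12 weeks to Week 103, so in that period follow-up is cut back to a scan scheduled 11 or 12 weeks earlier. No other section of the protocol or SAP restores the true order. At stake are the PFS and DOR estimates by disease group, where numbers are small.

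**Working it through.** The plan gives no figure on this point, so there is none to reproduce. The inputs are the SAP 8 imputation values, the last dose + 1 check, and the on-or-before condition of SAP 12.2 and 12.3. The gaps between dates are assumptions.

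**1. The rule applied literally.**
- Day missing: last dose 1 March 2017, progression 20 March, therapy truly 28 March but recorded as March 2017. The imputed start is 15 March. It is not before last dose, so it stands. It precedes 20 March, so the progression is censored.
- Year only: last dose 1 June 2017, progression 10 September, therapy truly 2 October but recorded as 2017. The imputed start is 30 June, and the progression is censored.
- The check can itself land too early: with last dose 17 March and progression 20 March, 15 March is replaced by 18 March, still before progression.

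**2. When the check protects.** If last dose is on or after progression, the imputed start cannot precede progression, and the error is 0%. If last dose is 1 day before progression, the error remains only when the imputed date equals the last dose date: at most about 3% of progression dates (day missing) or 0.3% (year only). If last dose is 2 or more days before, last dose + 1 is still earlier than progression and gives no protection.

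**3. Uniform dates, therapy truly after progression, same recorded period, last dose at least 2 days before progression.**
- Day missing, 30-day month: misordered when both fall on days 16 to 30, C(15,2)/C(30,2) = 105/435 = 24%.
- Year only: misordered when both fall in the 184 days after 30 June, C(184,2)/C(365,2) = 16,836/66,430 = 25%.

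**4. Fixed gaps.** Every progression date from 2016 to 2019 was used, with a partial therapy date and last dose 7 or more days before progression. Here the denominator is all progression dates, including those where therapy falls in the next month or year.

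| Progression to therapy | Day missing | Year only |
|---|---|---|
| 1 day | 47% | 50% |
| 7 days | 28% | 48.5% |
| 14 days | 5% | 46.5% |
| 21 days | 0% | 45% |
| 28 days | 0% | 43% |
| 60 days | 0% | 34% |

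**5. The reverse error.** Suppose therapy truly came first and progression second in the same period. If both fall on or before the 15th, the imputed start is on or after progression, and a record that should be censored becomes an event. The share is again C(15,2)/C(30,2) = 24%. For year only it is C(181,2)/C(365,2) = 16,290/66,430 = 25%.

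**6. Death.** Therapy starts on 6 March, recorded as March, and the subject dies on 10 March without documented progression. The imputed start is 15 March, so the death counts as an event although therapy came first. Capping the start at 10 March does not help, because a death on the therapy date still meets the on-or-before condition.

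**7. Effect of a lower bound at the progression date.** Misordering falls to 0% in every scenario of step 4. This follows by construction when therapy truly came second. When therapy truly came first in the same period, the bound makes every such progression an event, so the step 5 share rises from about a quarter to all.

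**The case against.** The strongest reply is that the route is narrow. It needs a partial therapy date, a last dose before progression, and both dates in the same recorded period. Protocol 3.6 continues treatment until progression or unacceptable toxicity, and subjects still dosing at progression are protected. The radiology row of Appendix 5 shows no entry at early termination, safety follow-up or in the follow-up phase, and protocol 4.4 describes follow-up after discontinuation as next therapy and survival. The footnote to that row is not in the available text, so how often progression is documented after last dose cannot be judged. SAP 9.6.6 will also summarise reasons for censoring. All of this stands and limits the size. It does not remove the defect: a tally of reasons does not show which therapy dates were imputed or misordered.

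A reader might infer more, and the documents do not support it:
- **That PFS and DOR are biased upwards.** Steps 5 and 6 create false events by the same mechanism, so the net direction is not established.
- **That about a quarter of subjects are exposed**, from the 40 of 161 (24.8%) in protocol 1.4.2.1 with AEs leading to study drug discontinuation. That figure does not show that both drugs stopped, and protocol section 3.0 provides for acalabrutinib alone after pembrolizumab ends. It shows only that last dose can precede progression, as do the toxicity holds of up to 28 days in protocol 3.8.1.
- **That one misordered record will move a Kaplan-Meier quartile.** That depends on where the event falls, and nothing in the documents settles it.

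**Conclusion.** The defect holds as a gap in a stated rule. Followed literally, SAP 8 with SAP 12.2 and 12.3 can turn a documented progression after last dose into censoring, for both PFS and DOR. The 24 to 25% is conditional on a partial date, uniform dates in the same recorded period, therapy truly after progression, and last dose at least 2 days before progression. It is not a share of all PFS or DOR events. With only the day missing, the effect disappears in the fixed-gap runs once therapy starts 21 or more days after progression; with only the year known it persists at 60 days. The number of partial dates is not given and may be zero. Severity is minor: the primary objective is safety, SAP section 5 plans no formal hypothesis test, and PFS and DOR are secondary and descriptive.

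**What to change.** In SAP 8, add for a partial start date of subsequent anticancer therapy:

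1. Where documented progression falls in the same known month or year, use the latest of the 15th or 30 June value, last dose + 1, and the progression date. The progression date is enough because the tables count progression on the day therapy starts; adding a day could move the start out of the recorded month.
2. Where no progression is documented and the imputed start would fall on or after death in that period, use the day before death, not earlier than last dose + 1 where possible. The rows of SAP 12.2 and 12.3 for therapy started before death then apply.
3. Flag these records in the PFS and DOR listings, and repeat both analyses under the present rule as a sensitivity check.

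While editing, state which drug's last dose is meant. Also reconcile the first paragraph of SAP 8 and protocol 5.4, which limit imputation to AE and concomitant medication dates, with the wider list in the second paragraph of SAP 8.

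The cost is a few sentences, a few lines of derivation code and one repeat run. The downside is that item 1 assumes therapy followed progression whenever the order is unknown. That keeps the event, and is wrong for subjects who truly started therapy first; the sensitivity run shows whether it matters.
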